Exclusion criteria	 Groups will be excluded if: they are run as part of NHS services; some of their regular members decline taking part in STORM-e and it is not possible to find alternative meeting times to run STORM-e. Participants will be excluded from the research if they do not meet any of the inclusion criteria or do not provide consent. 		
Intervention	STORM-e: web delivered adaptation of STORM, consisting of 4 weekly 90- minute sessions and a 90-minute follow-up session (delivered around four weeks after session 4).		
Primary objective of adaptation phase	To carefully adapt the STORM intervention to a web delivered version and pilot this to assess whether it is practical to deliver this version to established groups of people with ID in a range of community, social and educational settings. The findings will be used to inform the decision whether a subsequent feasibility trial is indicated (which may be a 3-arm trial of both versions of STORM, a 2 arm trial of one STORM version, or potentially no trial).		

Secondary objectives of adaptation phase	To assess the feasibility of collecting all planned outcome data digitally. To characterise 'Usual Practice' in a changed service delivery context.
Primary outcomes of adaptation phase	Adaptation phase: Acceptability of delivering STORM to groups in web delivered format
Secondary outcomes of adaptation phase	Adaptation phase: Feasibility of remotely collecting outcome and process data. Description of 'Usual practice' in a changed service delivery context.
Planned study period	Revised design to include 8 months for adaptation to STORM-e and piloting. 3 months for analysis and reporting.

2 Revised study summary & schema

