4.1.2 Other activities during months 1-4

Concurrently with adaptation of the manual, during months 1-4 the research team will also:

- (a) seek to characterise Usual Practice (UP). This will be achieved through an online survey of existing third sector organisations across the UK. Our survey will include questions about what discussion/conversation based group meetings are delivered, by whom, mode of delivery, location, and where UP has been modified in response to Covid-19, what changes have been made and how well they have worked. This survey will be delivered using Qualtrics and disseminated via our existing contacts, social media channels, and our partner organisations Mencap, the Foundation for People with Learning Disabilities and People First Dorset. We will also complete desk research on published and grey literature on virtual group support for people with ID during the current pandemic.
- (b) test digital delivery of the outcome measures at baseline. All procedures for supporting remote administration of study measures will be finalised as part of this adaptation phase. We will also draw on the experience of the first wave of data collection in a current UKRI/NIHR funded Covid-19 study of people with ID (research team members [name], [name] and [name] are project members). Any queries or difficulties will be resolved in collaboration with the self-advocate PPI advisers who have already provided input on the plans for outcome measurement during the earlier stages of this project. Digital administration of the outcome measures to all STORM-e pilot participants, along with evidence from parallel research studies, will inform the team whether it is feasible to collect outcome data for a feasibility trial using digital methods. If successful, this will mean we can re-consider our sampling procedures and expand the geographical regions we can recruit from for the feasibility trial.

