We will ask group facilitators to record group members' attendance at each session and occasions when group members experienced access and/or internet connection problems. Facilitators will also be asked to note down after each session challenges to delivering the intervention as intended and to participant engagement and to bring these notes for discussion in supervision. Feedback on how they addressed challenges and the impact will be elicited in supervision and shared with the research team. Additionally, we will use the session recordings to triangulate facilitators' records and assess what proportion of the sessions participants were able to attend (to account for participants dropping out at any point, either due to poor internet connection or for other reasons).

At the end of the last STORM-e session of each pilot group, our PPI advisors will act as peer researchers and co-lead a group discussion to obtain participants' views on STORM-e, what went well and what got in the way of their taking part and potentially benefitting from the intervention. They will explore whether ethical risks, including instances where individual participants needed practical or emotional support and risks to privacy during sessions, were managed in an acceptable manner. Postintervention outcome measures will be completed with all pilot participants as soon as is feasible after the last STORM-e session.

A researcher will interview each pilot group facilitator about their experiences of delivering STORMe. Interview data will be combined with supervision notes kept by the Mencap intervention lead to assess barriers and facilitators to STORM-e implementation.

During the pilot we will also test our revised plans for the process evaluation of STORM-e. This will include assessing the feasibility of recording of STORM-e sessions by facilitators locally and sharing of recordings with the research team to ensure compliance with data protection regulations. We will assess whether these recordings can be used to assess adherence and attrition or whether facilitator records need to be combined with review of session recordings to achieve this.

The outputs from Phase 1b will be:

(a) an adapted intervention manual for delivery of STORM-e that can be tested within a feasibility study;

(b) a revised logic model that incorporates what we have learnt during the pilot about mode of delivery and contextual factors;

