affected engagement
and/or raised concern.
Changes in this area could

≜UCL

make this more	
acceptable in the future.	

The risk of exclusion from STORM-e due to technical issues will be considered in relation to a target of no participant missing more than two sessions, or parts thereof (other than brief connectivity problems not exceeding 10 to 15 minutes), due to technical problems.

A decision whether it is feasible to collect outcome data remotely will be informed by responses to collection of baseline data during the pilot. Should 80%+ of collected outcome data be usable this will be deemed feasible, if 70%-79% of collected outcome data are usable we will review and revise the procedures for remote data collection. If less than 70% of collected outcome data are usable, we will consider with the SMG and SSC whether there are strategies to improve this (e.g., drawing on data from our UKRI/NIHR Covid-19 study with people with ID) or whether remote collection of data is not feasible.

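### The remote-data feasibility rule scores usable data as a share of data collected, not data due, so non-collection cannot by itself lower the score

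*Combined protocol and SAP*

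**What the plan says.** Section 4.1.4 (Phase 1c Decision phase) sets three bands for remote outcome data, all with collected data as the denominator:

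- Top: "Should 80%+ of collected outcome data be usable this will be deemed feasible".
- Middle: "if 70%-79% of collected outcome data are usable we will review and revise the procedures for remote data collection".
- Bottom: "If less than 70% of collected outcome data are usable, we will consider with the SMG and SSC whether there are strategies to improve this"; failing that, remote collection may be judged not feasible.

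The bands are introduced by this sentence: "A decision whether it is feasible to collect outcome data remotely will be informed by responses to collection of baseline data during the pilot".

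Elsewhere the target is wider. The secondary objective in the section 1 synopsis reads "To assess the feasibility of collecting all planned outcome data digitally". Section 4.1.2(b) plans measures for every pilot participant: "Digital administration of the outcome measures to all STORM-e pilot participants, along with evidence from parallel research studies, will inform the team" on feasibility for a later trial. Section 4.1.3 says that post-intervention "outcome measures will be completed with all pilot participants as soon as is feasible after the last STORM-e session".

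The documents set no completion or response-rate criterion for outcome measures. They define neither usable nor the unit being counted (item, measure or participant's assessment set).

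**The concern.** The question is whether data can be obtained remotely, but the rule measures the quality of what was obtained. A consented participant who could not be reached, or who provided nothing, does not appear in the calculation. A low completion rate and a high one can therefore give the same percentage and the same band.

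This matters because the top band is worded firmly, and consultation with the SMG and SSC is written into this rule only below 70%. Section 4.1.2(b) says that success would allow the team to reconsider sampling and recruit from a wider area, and section 4.1.3 lists data on the feasibility of remote collection as a pilot output. A favourable percentage that left out non-collection would mislead on both. By contrast, section 4.1.4 does set a target for sessions missed through technical problems; outcome assessment has no counterpart.

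**Working it through.** **Inputs from the documents.** Four groups averaging 5 members (sections 1 and 4.1.3): 4 × 5 = 20, which reproduces the planned N. Group size may run from 3 to 8 (section 1), so N could be 4 × 3 = 12 to 4 × 8 = 32. The 80% and 70% cut-offs are set by decision, so there is no derivation to reproduce.

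**Assumptions.** The documents give neither a completion rate nor a usability rate; those below are illustrative. One baseline set is counted per participant.

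**Formula.** usable/due = (usable/collected) × (collected/due). The plan scores only the first factor.

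**Step 1: 90% of collected data usable, N = 20.**
- 15 assessed: the rule reads 90%; of data due, 0.90 × 15/20 = 67.5% (lowest band).
- 12 assessed: the rule reads 90%; of data due, 0.90 × 12/20 = 54%.

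**Step 2: smallest usable count that still reaches 80% of collected, N = 20.**

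| Collected | Usable | % of collected | % of due | Band on data due |
|---|---|---|---|---|
| 20 | 16 | 80.0 | 80 | feasible |
| 18 | 15 | 83.3 | 75 | revise procedures |
| 16 | 13 | 81.3 | 65 | below 70% |
| 15 | 12 | 80.0 | 60 | below 70% |
| 12 | 10 | 83.3 | 50 | below 70% |
| 10 | 8 | 80.0 | 40 | below 70% |

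Every row passes as written. With half the sets collected, the smallest passing share of data due is 8/20 = 40%, and it is similar across the range of N: 5/12 = 42% and 13/32 = 41%.

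**Step 3: chance of reaching 80%.** Take N = 20, completion probability q, 90% usability among collected sets, and independent participants (a simplification, since they come in groups). As written, the chance is the sum over c of P(c of 20 collected) × P(at least 80% of c usable). On data due, it is P(X ≥ 16) with X binomial(20, 0.9q).

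| Completion q | As written | On data due |
|---|---|---|
| 50% | 0.87 | 0.002 |
| 60% | 0.88 | 0.015 |
| 70% | 0.90 | 0.086 |
| 80% | 0.91 | 0.30 |
| 90% | 0.91 | 0.67 |

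The rule as written hardly responds to completion; the slight rise comes from rounding to whole sets.

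**Step 4: what a due-based 80% would require.** Completion must be 0.80/u, where u is usability: 100% if u = 80%, 88.9% if u = 90%, and 80% if u = 100%.

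**The case against.** **The percentage is not the only input.** The decision is informed by baseline responses, and section 4.1.2(b) adds evidence from parallel studies. With about 20 people in four groups, several missing baselines would be obvious to the SMG. This stands in part: a reader might infer that a failed collection would be declared feasible, but the documents support only that the rule permits it. Room for judgement does not change the denominator.

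**Partial completers may not escape.** A reader might infer that anyone who stops part-way vanishes from the score. If the unit is a participant's assessment set, an incomplete set is collected and can be scored unusable, which lowers the percentage. It escapes only if the unit is the measure or item. This objection stands; the point is secure only for data not obtained at all.

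**Heavy non-collection is not shown.** Eligibility requires the ability to complete the measures with or without support, internet and device access, and help with web meetings where needed. Nothing in the documents supports a particular rate of missing baselines, or a claim that non-collection is the main way remote assessment fails. This stands, and the rates above are illustrations only. Eligibility makes non-collection less likely but does not ensure that an assessment takes place.

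**A new denominator resets the standard.** At 90% completion and 90% usability, the chance of passing falls from 0.91 to 0.67. Counting every consented participant also includes withdrawals unrelated to remote administration. Both stand as costs of the change.

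**Collected may have been meant loosely as planned.** That is possible, but nothing says so, and the word recurs in all three bands.

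**Conclusion.** The concern holds: the rule's denominator is narrower than the objective it serves, and low completion cannot by itself move the score. The denominator point rests on the text alone. Its size depends on assumed rates: at 90% usability and N = 20, the gap between the rule and the share of data due is 22.5 percentage points with 15 assessed (90 − 67.5) and 36 points with 12 assessed (90 − 54). If everything due is collected, the two figures coincide.

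The severity is moderate. Remote collection is a secondary objective, the SSC makes a recommendation to the funder, and the primary outcome of acceptability is unaffected. A reader might infer that a pass would automatically widen recruitment, but section 4.1.2(b) says only that the team could then reconsider sampling and expand the regions.

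**What to change.** 1. In all three bands of section 4.1.4, make the denominator the outcome data due: every planned measure for every consented pilot participant at the time point being scored.
2. State the counting unit and what makes data usable, including how a partly completed assessment is scored.
3. Report collected/due and usable/collected separately beside the combined figure.
4. Tabulate reasons for non-collection, so that withdrawals unrelated to remote administration can be told apart from failures of remote contact or connection.
5. Have the sponsor confirm that 80% and 70% are meant to apply to data due.

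The cost is a short wording change, two definitions and a count of measures due. For a given definition of unit and usable, the reported percentage can only stay the same or become less favourable. The real cost is the stricter standard, which is why the cut-offs need a deliberate decision and should not simply be carried over.
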